5.7.3. Subgroup Analyses

Subgroup analysis by gender, symptomatic vs. asymptomatic, race (white vs. other), and baseline viral load (above or below median) may be performed in seronegative mFAS in order to assess the consistency of results.

5.7.4. Dose Response Modelling

Several dose response models will be explored for the TWA of change in baseline in viral load (\log_{10} copies/mL) from day 1 to day 7, and then a single model is selected using Akaike's Information Criteria (AIC). The AIC considers a trade-off between increasing the number of parameters in terms of goodness-of-fit by introducing a penalty for the number of parameters. The model with the lowest AIC value is selected. The models under consideration are linear, hyperbolic E_{max} , and sigmoidal E_{max} . Additional models may be considered. As the dose response testing and modelling is for estimation, there will be no adjustment for multiplicity.

Table 4: Set of Candidate Dose Response Models

Name	Model	Description
Sigmoidal E_{max}	$y_i = E_0 + E_{max} \frac{D_i^h}{ED_{50}^h + D_i^h} + \epsilon_i$	
i: the patient ID y_i: the response for the i^{th} patient E_0: the placebo effect E_{max}: The maximum effect attributable to the drug ED_{50}: The dose that produces one-half of E_{max} h: The hill parameter and determines the steepness of the slope D_i: The dose-level for the i^{th} patient ϵ_i: The error term for the i^{th} patient where each error term is independent and identically Normally distributed with mean 0 and standard deviation σ.

Hyperbolic E_{max}	$y_i = E_0 + E_{max} \frac{D_i}{ED_{50} + D_i} + \epsilon_i$	Special case of above model where $h = 1$
Linear	$y_i = E_0 + \beta_1 * D_i + \epsilon_i$	β_1 : Linear effect term
Exponential	$y_i = E_0 + E_1 \left(\exp\left(\frac{D_i}{\delta}\right) - 1 \right) + \epsilon_i$	
E_1: Exponential term δ: Scale

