### 3.2.2. Rationale for Dose Selection

Initial phase 1 and phase 2 studies in outpatients with SARS-CoV-2 infection (Study COV-2067) assessed single IV dose administration of REGN10933+REGN10987 at 2400 mg (1200 mg per mAb) and 8000 mg (4000 mg per mAb). The original strategy in selecting these doses was to identify a target concentration in lung epithelial fluid (ELF) that approximates the effective concentration required for 99% viral neutralization ( $EC_{99}$ )\* of SARS-CoV-2 in vitro, and then identify doses anticipated to meet or exceed this concentration in lung ELF. Using observed  $EC_{99}$  estimates of 0.14  $\mu\text{g/mL}$  (REGN10933) and 0.78  $\mu\text{g/mL}$  (REGN10987), assuming drug concentration in lung ELF to be 0.15x that of serum (Magyarics, 2019), and accounting for uncertainties related to drug PK and mAb penetration into lung ELF, 20  $\mu\text{g/mL}$  (per mAb) was selected as the initial target concentration in serum, and a 2400 mg dose was chosen with the assumption that  $\geq 95\%$  of patients would exceed the target concentration in serum for at least 28 days. An 8000 mg dose also was evaluated, in the event that a higher dose was required for efficacy.

Data from the phase 1 and phase 2 studies confirmed that  $\geq 95\%$  of patients exceeded 20  $\mu\text{g/mL}$  per mAb in serum for 28 days at the 2400 mg dose, and dose-proportional increases in exposure were observed at 8000 mg. Moreover, treatment with either 2400 mg or 8000 mg REGN10933+REGN10987 reduced viral load and led to positive trends in clinical outcomes, as demonstrated by similar and significant reductions in COVID-19-related MAVs at both dose levels (Weinreich, 2020)(for more information, refer to the Investigator's Brochure). Based on the flat dose response observed for the 2400 mg and 8000 mg doses, as well as a linear PK relationship between the doses, the 2400 mg IV dose was chosen as the highest dose to be investigated in phase 3 of Study COV-2067. A 1200 mg IV dose is also being investigated in that study and is expected to achieve approximately 50% of the concentrations observed for 2400 mg, assuming that the linear PK relationship between 2400 mg and 8000 mg is also observed at this lower dose.

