#### 11.4.4. Control of Multiplicity

The overall type I error rate will be controlled for the primary hypothesis at the two-sided 0.05 level by the use of a step-down testing approach, starting at the top dose (Table 4). Each test compares a specific treatment group to pooled placebo. The highest dose will be tested first; if significant, the second highest dose will be tested; and so on. No multiplicity adjustments will be made for secondary endpoints, nor for comparisons between active doses.

Table 4: Statistical Testing Hierarchy

Hierarchy Number	Description
1	2400 mg IV versus pooled placebo
2	1200 mg IV versus pooled placebo
3	1200 mg SC versus pooled placebo
4	600 mg IV versus pooled placebo
5	600 mg SC versus pooled placebo
6	300 mg IV versus pooled placebo

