2.2. Power Considerations

The sample size is based on the primary virologic endpoint of the time-weighted average (TWA) daily change from baseline in viral load (\log_{10} copies/mL) from day 1 to day 7, in patients who are seronegative and who have a positive RT-qPCR value at baseline. In the Phase 2 portion of Study R10933-10987-COV-2067, the mean (SD) was -0.73 (0.948) \log_{10} copies/mL (see Investigator's Brochure). For the primary hypothesis comparing each dose to placebo, approximately 57 patients per treatment group will provide ~98% power to detect a difference of -0.73 \log_{10} copies/mL between any active treatment group and placebo. In order to enroll 400 seronegative patients, the study will randomize approximately 800 patients, assuming that 50% are seronegative.

[figure not shown]
For comparisons between doses and regimens, the study plans to enroll 700 seronegative patients in order to have 100 patients per group. For between-group comparisons, the 95% CI half-width between any two treatment groups with 100 patients per group would be 0.27 \log_{10} copies/mL. In order to enroll 700 seronegative patients, approximately 1400 patients will be randomized.

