5.7. Hypothesis Test

The statistical hypothesis for the primary virologic efficacy endpoint is:

H_0 : There is no difference between patients treated with one or more dose regimens of REGN10933+REGN10987 and patients treated with placebo in time weighted average daily change from baseline in viral load from day 1 to day 7

H_1 : REGN10933+REGN10987 reduces time weighted average daily change from baseline in viral load (\log_{10} copies/mL) from day 1 to day 7, relative to placebo

The type I error rate is 0.05.

[figure not shown]

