11.3. SAS Code for Dose Response Modelling

We utilize SAS code from the chapter on Classical Dose-Response Study from *Modern Approaches to Clinical Trials Using SAS®: Classical, Adaptive, and Bayesian Methods* edited by Sandeep M. Menon and Richard C. Zink (page 185). We assume the data set data1 contains the response for each dose and use arbitrary initial values for demonstration purposes.

```
*** Sigmoidal E_max model;
proc nlmixed data=data1 alpha=0.05;
  *** set up initial values
  parms e0=10 emax=80 ed50=5.5 h=1 v=400;
  *** Specify that ed50 must be positive;
  bounds ed50>0;
  *** Define model;
  if dose=0 then eta = e0;
  else eta = e0 + (emax*dose**h) / (ed50**h+dose**h);
  model resp ~ normal(eta, v);

  *** Estimate the difference in means;
  estimate "Diff Means (dose 2400 mg – placebo)"
    e0+((emax*2400**h)/(ed50**h+2400**h))-e0;
  estimate "Diff Means (dose 1200 mg – placebo)"
    e0+((emax*1200**h)/(ed50**h+1200**h))-e0;
  estimate "Diff Means (dose 600 mg – placebo)"
    e0+((emax*600**h)/(ed50**h+600**h))-e0;
  estimate "Diff Means (dose 300 mg – placebo)"
```

$e0 + ((\text{emax} * 300 ** h) / (\text{ed}50 ** h + 300 ** h)) - e0;$

predict eta out=etahat;

****output estimations;

****dataset est has output for estimate of the mean differences;

****dataset parms has output for parameters: e0 emax ed50 h;

ods output AdditionalEstimates=est ParameterEstimates=parms;

run;

*** Hyperbolic E_max model;

proc nlmixed data=data1 alpha=0.05;

*** set up initial values

parms e0=10 emax=80 ed50=5.5 v=400;

*** Specify that ed50 must be positive;

bounds ed50>0;

*** Define model;

if dose=0 then eta = e0;

else eta = e0 + (emax*dose) / (ed50+dose));

model resp ~ normal(eta, v);

*** Estimate the difference in means;

estimate "Diff Means (dose 2400 mg – placebo)"

$e0 + ((\text{emax} * 2400) / (\text{ed}50 + 2400)) - e0;$

estimate “Diff Means (dose 1200 mg – placebo)”

$e0 + ((\text{emax} * 1200) / (\text{ed}50 + 1200)) - e0;$

estimate “Diff Means (dose 600 mg – placebo)”

$e0 + ((\text{emax} * 600) / (\text{ed}50 + 600)) - e0;$

estimate “Diff Means (dose 300 mg – placebo)”

$e0 + ((\text{emax} * 300) / (\text{ed}50 + 300)) - e0;$

predict eta out=etahat;

****output estimations;

****dataset est has output for estimate of the mean differences;

****dataset parms has output for parameters: e0 emax ed50;

ods output AdditionalEstimates=est ParameterEstimates=parms;

run;

*** Linear model;

proc nlmixed data=data1 alpha=0.05;

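### The AIC-selected dose-response curve's nominal 95% intervals ignore the selection step and can miss the 300 mg and 600 mg effects far too often if the curve bends within the tested dose range

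*SAP*

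**What the plan says.** SAP 5.7.4 names linear, hyperbolic Emax and sigmoidal Emax models. Its Table 4 adds an exponential model, and the text leaves room for more. The rule is "The model with the lowest AIC value is selected". The section describes the work as estimation and makes no multiplicity adjustment.

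SAP 11.3 fits each candidate on its own, with calls of the form "proc nlmixed data=data1 alpha=0.05". Each call has estimate statements for 2400, 1200, 600 and 300 mg minus placebo, and the results are saved. Neither section mentions model averaging, resampling, or that an interval is conditional on the chosen curve.

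Two other places bear on the point. SAP 5.7.1 separately plans ANCOVA differences from pooled placebo, with 95% intervals, for every dose group. Protocol 3.2.2 chose the top phase 3 dose of the earlier outpatient study in these terms: "Based on the flat dose response observed for the 2400 mg and 8000 mg doses".

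**The concern.** An interval computed as if the winning curve had been fixed in advance leaves out the uncertainty about which curve is right. The error is one-sided in an awkward way. The linear model has the fewest parameters, so AIC tends to choose it when the data cannot clearly show curvature. That same model gives by far the tightest interval at low doses.

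SAP 2.1 says the study is meant to find the lowest regimen with virologic efficacy like that of 2400 mg IV. A curve that shows 300 mg as nearly inert, with a tight interval, could therefore mislead on the very question the modelling serves. The reader would also hold two conflicting intervals for the same dose, with no rule on how to weigh them.

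**Working it through.** **Inputs from the documents.** Effect -0.73 and SD 0.948 log10 copies/mL; 57 per group (about 400 seronegative patients over 7 groups) or 100 per group (700 over 7), all from SAP 2.2; 95% intervals; doses 0, 300, 600, 1200 and 2400 mg.

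**Assumed.** The shape of the true curve, a 2400 mg effect of -0.73, and no covariates (the SAP 11.3 code has none).

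**1. The plan's own figures.** SAP 2.2 states "approximately 57 patients per treatment group will provide ~98% power to detect a difference of -0.73".
- SE = 0.948 × √(2/57) = 0.178, and 0.73/0.178 = 4.11. Power = Φ(4.11 - 1.96) = 98.4%, which agrees.
- SAP 2.2 also states "the 95% CI half-width between any two treatment groups with 100 patients per group would be 0.27". 1.96 × 0.948 × √(2/100) = 0.263, about 2% below the stated value.
- At 57 per group the same pairwise half-width is 0.35.

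**2. Half-width under the linear model.** The mean dose is 900, and the squared deviations sum to 810,000 + 360,000 + 90,000 + 90,000 + 2,250,000 = 3,600,000 per patient per arm. Half-width at 300 mg = 1.96 × 300 × 0.948/√(57 × 3,600,000) = 0.039. That is about one-ninth of 0.35.

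**3. Where the linear fit is centred.** For a hyperbolic curve the true 300 mg effect is -0.73 × [(ED50 + 2400)/2400] × [300/(ED50 + 300)]. With ED50 300 mg this is -0.41. The true means at 300, 600, 1200 and 2400 mg are then -0.411, -0.548, -0.657 and -0.730. The expected least-squares slope is (600 × 0.411 + 300 × 0.548 - 300 × 0.657 - 1500 × 0.730)/3,600,000 = -0.000245 per mg, so the line puts 300 mg at -0.07. The gap of 0.34 is more than eight half-widths, so the linear interval cannot realistically cover.

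**4. Simulation.** 4,000 trials per scenario. Linear, hyperbolic and sigmoidal models were fitted by maximum likelihood, the lowest AIC was taken, and the interval was that model's delta-method Wald 95% CI. Monte Carlo SE is about 0.3-0.8 points.

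| True curve | True 300 mg effect | Misses at 300/600 mg, 57 per arm | 100 per arm |
|---|---|---|---|
| Hyperbolic, ED50 50 mg | -0.64 | 6/6% | not tabulated |
| ED50 150 mg | -0.52 | 8/7% | about 6/5% |
| ED50 300 mg | -0.41 | 14/13% | 8-9/7% |
| ED50 600 mg | -0.30 | 29/28% | 14/13-14% |
| ED50 1200 mg | -0.22 | 51/50% | 35/33% |
| Sigmoidal, ED50 300, h=4 | -0.37 | 8-9/6% | about 8/5%* |
| Sigmoidal, ED50 600, h=2 | -0.16 | 38/34% | about 27/19%* |
| Linear | -0.09 | 10-11/7-8% | about 14/10%* |

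*Run with the exponential model among the candidates.

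Adding the exponential model at 57 per arm, or pooling SC with IV at 600 and 1200 mg, does not change the conclusion. With both changes, ED50 600 mg gives about 23/22%.

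**5. Cause.** Across separate runs at 57 per arm, AIC picked the linear model in about 9-12%, 22-26% and 44-46% of trials at ED50 300, 600 and 1200 mg. Its 300 mg interval essentially never covered. At ED50 600 mg that explains about 24 of the 29 points.

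**6. Comparators at 57 per arm.** Pairwise group contrasts covered about 94-96% in every scenario. The true hyperbolic model fixed in advance covered 90-96%, so part of the shortfall is the Wald approximation rather than selection.

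**7. The remedy.** A bootstrap that refits every candidate and repeats the selection covered 91-97% at 300 and 600 mg across hyperbolic and sigmoidal truths. AIC-weighted averaging within a bootstrap did well except under a steep, late sigmoid (70% at 300 mg).

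**The case against.** The best defence is that little rests on these curves. Protocol 11.4.3.1 introduces the modelling as exploration, SAP 5.7.4 calls it estimation, and no decision rule uses the model intervals. Protocol 11.4.4 confines its claim: "The overall type I error rate will be controlled for the primary hypothesis at the two-sided 0.05 level". SAP 5.7.1 already gives ANCOVA intervals for every dose against pooled placebo and between active doses, so an implausible linear fit at 300 mg would sit beside an interval that exposes it. This stands, and it limits the point to the supporting estimates.

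Second, SAP 5.7.4 does not say in words that the selected curve's intervals will be reported, and SAP 11.3 presents its code as a demonstration. This also stands: reporting is inferred from the 0.05 setting and the saved estimates, though it is the natural use of that output.

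Third, the earlier flat response makes the largest ED50 values less likely. At ED50 1200 mg, 2400 mg reaches 2400/3600 = 67% of Emax and 8000 mg reaches 8000/9200 = 87%. At ED50 300 mg the figures are 89% and 96%. So the top of the miss range deserves less weight. The same finding, however, sits badly with keeping linear and exponential curves as candidates.

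A reader might infer that these intervals fail whenever dose matters. The calculations do not support that. At ED50 150 mg the 300 mg dose has only 0.517/0.73 = 71% of the 2400 mg effect, yet the misses are 7-8%. A reader might also infer that the trial's conclusions on low doses are unreliable. The planned ANCOVA analysis does not depend on the curve.

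**Conclusion.** The point holds within limits. The plan makes no allowance for choosing the curve. If the response bends within the tested range (ED50 roughly 300-1200 mg), the nominal 95% intervals at 300 and 600 mg miss in about 13-50% of trials at 57 per arm and about 7-35% at 100 per arm. For ED50 up to 150 mg the misses are about 6-8% at 57 per arm, which is tolerable for supporting estimates.

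These ranges rest on an assumed hyperbolic shape and on a 2400 mg effect of -0.73. Sigmoidal shapes can do better or worse. Only the dose-response estimates are affected. The primary contrasts, their intervals and the step-down tests stand as planned.

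**What to change.** In SAP 5.7.4, close the candidate list, with text and Table 4 in agreement, and say which arms enter the fit. State that intervals for the selected curve come from a bootstrap in which every candidate is refitted and the AIC selection repeated in each resample. Give the resampling scheme and the number of resamples. Replace the single-fit Wald intervals in SAP 11.3 accordingly, and present the new intervals beside the ANCOVA intervals for the same doses. AIC-weighted averaging within the same bootstrap may be added as a sensitivity analysis.

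Fixing hyperbolic Emax alone is not a safe substitute. With profile-likelihood intervals at 57 per arm and a sigmoidal truth (ED50 1000 mg, h=3), its coverage at 300/600 mg was 1/55%, against about 18/74% for the current rule.

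The cost is SAP wording, some programming in R (already listed in SAP 9), and wider model-based intervals: half-widths of about 0.19-0.32 in the bootstrap runs under hyperbolic curves, against 0.04 when the linear model wins at 57 per arm. Patients and data collection are unaffected.

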5.7.5. Analysis of Secondary Efficacy Variables

For the analysis of primary and secondary efficacy variables, the table below summarizes the quantities and corresponding methods for analysis. The details of methods are described the paragraphs that follow.

Table 5: Secondary Efficacy

Measurement	Units	Metric	Method
Viral load (D1-5)	log ₁₀ copies/mL	TWA	ANCOVA
Viral load	log ₁₀ copies/mL	Change from BL in viral load at each visit	MMRM
Viral load	log ₁₀ copies/mL	Proportions <LLOQ, <LOD, >10 ⁴ , >10 ⁵ , >10 ⁶ , or >10 ⁷	Fisher's Exact Test/Logistic Regression
Percent change in Viral Load	copies/mL	Percent change in viral load (copies/mL) to each time point	MMRM

A mixed effect model for repeated measures (MMRM) will assess the time course of treatment effect in viral load, the change from baseline in viral load (log₁₀ copies/mL) at each visit for both the Seronegative mFAS and the Overall mFAS populations. The model will include terms for baseline, treatment, visit, treatment-by-baseline interaction, baseline-by-visit interaction, and treatment-by visit interaction. Within-patient errors will be modeled with an unstructured covariance matrix; heterogeneous autoregressive (1), or compound symmetry covariance matrix will be considered in that order if a model does not converge. The least squares means estimates for the mean at each visit and mean change from baseline to each visit as well as the difference of these estimates between each anti-spike mAb treatment arm and placebo will be provided along with the corresponding standard error, p-value, and associated 95% confidence interval.

In the Seronegative mFAS, the proportion of patients who have PCR below the limit of detection (LOD), below the lower limit of quantification (LLOQ), or have qPCR levels >10⁴, >10⁵, >10⁶, or >10⁷ will be tabulated over time. The numbers of patients in each category will be tested using Fisher's Exact test. Corresponding p-values and confidence intervals will be presented.

There may be additional analysis of the proportions of patients who have PCR below the limit of detection, below the lower limit of quantification, or have quantitative PCR levels above >10⁴, >10⁵, >10⁶, or >10⁷ will be tabulated over time using logistic regression model with terms for treatment arm, baseline viral load, and the treatment-by-baseline viral load interaction. Adjusted odds ratios and corresponding p-values and confidence intervals may be estimated from the model.

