#### 11.4.3.2. Secondary Efficacy Analysis

A mixed effect model for repeated measures (MMRM) will assess the time course of treatment effect in viral load, the change from baseline in viral load ( $\log_{10}$  copies/mL) at each visit for both the Seronegative mFAS and the Overall mFAS. There will be terms for baseline, treatment, visit, treatment-by-baseline interaction, baseline-by-visit interaction, and treatment-by visit interaction. Within-patient errors will be modeled with an unstructured, heterogeneous autoregressive (1), or compound symmetry covariance matrix in that order if a model does not converge. The least squares means estimates for the mean at each visit and mean change from baseline to each visit as well as the difference of these estimates between each anti-spike mAb treatment arm and placebo will be provided along with the corresponding standard error, p-value, and associated 95% confidence interval.

In the Seronegative mFAS, the proportion of patients who have PCR below the limit of detection (LOD), below the lower limit of quantification (LLOQ), or have qPCR levels  $>10^4$ ,  $>10^5$ ,  $>10^6$ , or  $>10^7$  will be tabulated over time. The numbers of patients in each category will be tested using Fisher's Exact test. Corresponding p-values and confidence intervals will be presented.

Analyses of the virologic endpoints with in the Overall mFAS population will also be performed in subsets defined by the baseline viral load ( $>10^4$  copies/mL,  $>10^5$  copies/mL,  $>10^6$  copies/mL,  $>10^7$  copies/mL). The TWA, the time course of change, and other virologic endpoints will be summarized and/or analyzed within each of these categories.

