1.2.5. Modifications from the Statistical Section in the Final Protocol

Not applicable.

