4.5. Efficacy Variable

4.5.1. Primary Efficacy Variable

The primary efficacy measurement is the viral load of patients in the Seronegative mFAS as measured by central laboratory RT-qPCR (\log_{10} copies/mL). The primary efficacy variable is the time-weighted average (TWA) change from baseline in viral load (\log_{10} copies/mL) from day 1 to day 7 as measured by RT-qPCR in NP swabs. The TWA is calculated using the trapezoidal rule as the area under the curve (AUC) divided by this observational period as follows:

$$TWA = AUC / (t_k - t_1) = \left[\sum_{i=2}^k (t_i - t_{i-1}) * (V_i + V_{i-1}) / 2 \right] / (t_k - t_1)$$

where V_i is the result of change in viral load (\log_{10} copies/mL) at time point t_i from baseline. As baseline is time point t_1 , then $V_1 = 0$.

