4.5.2. Secondary Efficacy Variables

The table below describes the primary and secondary efficacy variables labelled ‘P’ or ‘S’, respectively. An ‘X’ means that variable will not be analyzed. The two columns on the far right describe the analysis sets for the efficacy analysis.

Table 2: Efficacy Variables

Efficacy Variable	Endpoint Type	Baseline Viral Load Subgroup	Seronegative mFAS	Overall mFAS
Change from BL in viral load – TWA (days 1 to 7)	Continuous	All	P	S
	Continuous	>10 ⁴ copies/mL	X	S
	Continuous	>10 ⁵ copies/mL	X	S
	Continuous	>10 ⁶ copies/mL	X	S
	Continuous	>10 ⁷ copies/mL	X	S
Change from BL in viral load – TWA (days 1 to 5)	Continuous	All	S	S
	Continuous	>10 ⁴ copies/mL	X	S
	Continuous	>10 ⁵ copies/mL	X	S
	Continuous	>10 ⁶ copies/mL	X	S
	Continuous	>10 ⁷ copies/mL	X	S
Proportion of patients with viral load >10 ⁴ copies/mL at each visit	Categorical	All	S	S
Proportion of patients with viral load >10 ⁵ copies/mL at each visit	Categorical	All	S	S
Proportion of patients with viral load >10 ⁶ copies/mL at each visit	Categorical	All	S	S
Proportion of patients with viral load >10 ⁷ copies/mL at each visit	Categorical	All	S	S
Proportion of patients <LLOQ	Categorical	All	S	S
Proportion of patients <LOD	Categorical	All	S	S
Change from BL in viral load at each visit	Continuous	All	S	S

Denote baseline as BL, Limit of Detection as LOD, and Lower Limit of Quantification as LLOQ.

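### SAP Table 5 adds an MMRM of percent change in viral load (copies/mL) that no endpoint list contains and no text specifies; fitted on that scale it would be inefficient and driven by a few rebounding patients

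*SAP*

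**What the plan says.** SAP 5.7.5, Table 5, has two MMRM rows. One is the change from baseline in log10 copies/mL at each visit. The other has copies/mL in the units column and "Percent change in viral load (copies/mL) to each time point" as its metric. The sentence introducing the table says "The details of methods are described the paragraphs that follow", but only one MMRM paragraph follows, and its response is "the change from baseline in viral load (log₁₀ copies/mL) at each visit for both the Seronegative mFAS and the Overall mFAS populations". That paragraph gives model terms, a covariance order and outputs (standard error, p-value and 95% CI for each arm against placebo). Percent change is not mentioned again.

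The declared per-visit continuous variable is the log10 change (Protocol 4.2, SAP 1.2.4). SAP Table 2 lists "Change from BL in viral load at each visit" and has no percent-change row. In Protocol 11.4.3.2, "A mixed effect model for repeated measures (MMRM) will assess the time course of treatment effect in viral load", again on log10 change only. SAP 1.2.5, which records modifications from the protocol's statistical section, reads "Not applicable".

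**The concern.** Two programmers could produce different tables from this row. One might back-transform the log10 MMRM. The other might fit a new normal-error MMRM to raw percent change. The separate row and the separate unit favour the second reading.

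On the raw scale, a patient who clears virus sits near -100% and a patient who rises by 2 log10 sits at +9,900%. SAP 7.2 adds to the skew: nondetectable RNA is set to 0 log10 copies/mL, and the highest value is kept when several fall at one visit. A mean on this scale depends on the few patients whose load rises. The resulting table could show no effect, or an effect in the wrong direction, next to a clear log10 result. The study's stated purpose is to find a lower dose with similar virologic efficacy, so a noisy arm-by-arm table could mislead on dose ranking.

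**Working it through.** **Inputs from the documents.** TWA difference -0.73 log10, SD 0.948, 57 per group, power about 98%, and 100 per group at full enrollment (Protocol 11.2, SAP 2.2). Two-sided 0.05 (Protocol 11.4.4). NP swabs on days 1, 3, 5 and 7 (schedule of events). The documents give no per-visit SD and no placebo mean change, so these are assumed and shown as ranges.

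**The plan's own figure.** 0.73 / (0.948 × √(2/57)) = 4.11, and Φ(4.11 - 1.96) = 98.4%. The stated figure of about 98% reproduces.

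**Effect of one patient.** Suppose 56 of 57 patients are at -100% and one rises by k log10 (an assumption). The arm mean is (56 × (-100) + 100 × (10^k - 1)) / 57:
- k = 1: -82%
- k = 2: +75%
- k = 3: +1,654%

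**Range for the per-visit SD.** SAP 4.5.1 defines the summary: "The TWA is calculated using the trapezoidal rule as the area under the curve (AUC) divided by this observational period as follows". With V1 = 0, the weights on days 3, 5 and 7 are 1/3, 1/3 and 1/6, which sum to 5/6. With a common SD and between-visit correlation ρ, per-visit SD = 0.948 / √(0.25 + 0.444ρ). This gives 1.14, 1.38 and 1.53 for ρ = 1, 0.5 and 0.3. The TWA SD of 0.948, used directly, is the most favourable case.

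**Simulation.** At least 20,000 trials per setting, normal log10 change, visit difference 0.73, and an unadjusted t-test in the correct direction on log10 change and on 100 × (10^change - 1). Repeat runs agree to about one point.

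| Assumed per-visit SD | 0.948 | 1.14 | 1.53 |
|---|---|---|---|
| Power, log10, 57 per arm | 98% | 92% | 72% |
| Power, percent, 57 per arm | 44% | 23% | 7% |
| Wrong sign, percent, 57 per arm | 3% | 7% | 17% |
| Median share of placebo total from two largest patients | 47% | 58% | 73% |
| Power, percent, 100 per arm | 62% | 35% | 10% |

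The placebo total is the sum of follow-up/baseline ratios. These rows do not depend on the assumed placebo mean: moving it multiplies every ratio in both arms by the same constant, which leaves the t statistic and the shares unchanged. The sign of the placebo arm mean does depend on it. At a placebo mean of -1.5 log10, that arm mean is positive in about 3, 24 and 86% of arms.

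**TWA effect converted to a constant visit effect.** 0.73 / (5/6) = 0.876 log10. With 57 per arm and SD 1.14 to 1.53, power is 98 to 85% on log10 and 31 to 9% on percent.

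**Baseline adjustment.** Adding baseline and treatment-by-baseline terms at a single visit (difference 0.73, 57 per arm, baseline-change correlation -0.5) gives 99.7% versus 48% at SD 0.948, and 82% versus 8% at SD 1.53. A second set of assumptions (baseline mean 6.5, SD 1.7, slope -0.4, floor at 0 log10) gives 98% versus 26 to 27% at SD 0.948. The adjusted figure moves with the assumptions; the gap does not close.

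**The case against.** - **A back-transformation may have been meant.** The text after Table 5 describes one MMRM, on log10 change, and the primary and dose-response analyses are on log10 as well. Under that reading the inefficiency disappears and only a sentence is missing. This is plausible, and the power figures hold only for a raw-scale fit. But nothing in the SAP says so, and the row has its own unit.
- **The terms and covariance could be borrowed from the existing paragraph.** They could. The response scale, any transform, the scale of the baseline covariate and the analysis set would still be undefined.
- **The analysis is pre-specified by being in the SAP, and a SAP may add supportive analyses.** True. What remains is that Table 5 disagrees with both endpoint lists and with SAP Table 2, and that SAP 1.2.5 records nothing.
- **The output is secondary.** This stands. Protocol 11.4.4 says "No multiplicity adjustments will be made for secondary endpoints, nor for comparisons between active doses", and the log10 MMRM will be reported for the same visits.
- **The size depends on assumed SDs and a one-visit test.** Also true: percent-scale power runs from 44% to 7% across the SDs at 57 per arm. It is higher at 100 per arm but stays far below the log10 result. A floor at 0 log10 did not remove the gap.

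**Conclusion.** The concern holds. The row appears in no endpoint list, is not recorded as a change from the protocol, and has no stated response scale. If it is fitted on raw percent change, as the unit and separate row suggest, power at 57 per arm falls from 98-72% to 44-7%, and the estimate points the wrong way in 3-17% of trials. These figures assume normal log10 change, a visit difference of 0.73 log10 and per-visit SDs of 0.948 to 1.53. A misleading mean increase in an arm is possible but not certain; it depends on the placebo mean, which the documents do not give. The consequence is confined to one unadjusted secondary output. The primary TWA ANCOVA and its hierarchy are unaffected. This should be corrected but does not threaten the trial's main conclusion.

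**What to change.** Delete the row, or define it as a back-transformation of the planned log10 MMRM and fit no separate model:
- percent change in an arm = 100 × (10^LSmean - 1);
- treatment ratio = 10^(LS-mean difference), with the confidence limits transformed in the same way. For example, 10^-0.73 = 0.19, that is, 81% lower than placebo.

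If the row is kept, add it to SAP Table 2 with its analysis set and record it in SAP 1.2.5. The cost is one table row and, if it is kept, an entry in each of those two places. No new data and no extra model are needed.
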